1. STUDY SUMMARY

Title	ICU-related Out of Pocket Expenses (ICOPE) – a multinational prospective study in African and Asian countries		
Sponsor	Mahidol Oxford Tropical Research Unit Collaboration for Research, Implementation and Training in Critical Care in Asia and Africa (CCAA)		
Funder	Wellcome		
Trial design	Prospective observational study		
Trial Participants	All patients admitted to the participating ICUs during a predefined window of 14 days and expected to have a duration of stay >24 hours. Exclusion criteria is lack of informed consent.		
Sample size	at least 354 patients (at least 212 non-ventilated & 142 ventilated patients)		
Planned study period	Recruitment during 14 days Follow up until ICU discharge for each recruited patient, at 30 days after admission and 6 months after admission. Total study duration: 18 months		
Planned recruitment period	From 01 Dec 2023 to 30 June 2024		
	Objectives	Endpoints	Timepoint(s) of evaluation
Primary objective	To quantify ICU care related OOPE in African and Asian LMICs and the proportion of patients/families facing CHE, comparing patients receiving invasive ventilation to non-ventilated patients.	1.Costs per complete patient episode, as actually spent in US dollars and International dollars (purchasing power parity exchange rate) in ventilated versus non-ventilated groups. 2.Relative risk of CHE in ventilated versus non-ventilated groups.	During ICU stay, average 1 week
Secondary objectives	To identify risk factors for CHE.	Risk factors for CHE	Not applicable
	To identify coping strategies for OOPE and CHE	Frequency of different coping strategies for financial coverage of ICU costs	During ICU stay and follow up, 6 months

2. BACKGROUND AND JUSTIFICATION

2.1 Increasing availability and access to ICU care in LMICs

Availability and utilization of intensive care unit (ICU)-level care is increasing in low and middle income countries (LMICs). In parallel, there is a rise in the financial burden for service providers, but also for patients and their families. Even in LMIC healthcare systems which offer government funded healthcare, ICU is associated with considerable costs which impact patients' households. As such, stakeholders seeking to expand access to health services must consider the financial burden associated with critical care becoming routinely available. In fact, increasing health coverage is paradoxically associated with worsening out of pocket expenses.¹ Achieving universal health coverage, including financial risk protection, is a target of the 3rd Sustainable Development Goal.^{2,3} Critical care relates both to acute conditions (injury, trauma, infection, etc.) and chronic diseases. Return on investment for these conditions may be different leading to cost-effectiveness considerations.

2.2 ICU costs

ICU admission is often unexpected, the treatment and interventions needed are usually unpredictable and length of stay frequently prolonged. In fact, a single ICU admission can cost from few hundreds to more than one hundred thousand US dollars.⁴ Thus ICU care often results in spiraling costs, which if not absorbed by welfare or insurance systems, directly fall on the patient and family. Costs can be classified as direct and indirect costs, with direct cost further divided in 'medical' and 'non-medical' domains. *Direct* medical costs include any daily fixed costs for the ICU bed, consumables (eg. medications, laboratory tests, nutrition, fluids, bandaging, ventilation circuits) which often fall at the pocket of patients and families. Studies assessing ICU direct costs are available from LMICs such as Brazil, Thailand, Vietnam and India.⁵⁻⁸ Direct non-medical costs include transportation and accommodation. In addition, *indirect costs* arise such as loss of income for patients, especially ones employed without sick leave cover. For families and caregivers, income loss and productivity loss are associated with time spent being at the hospital with their relatives.

2.3 Out of pocket and catastrophic health expenditure

ICU care in LMICs is mostly funded by a mixed system of public welfare, insurance coverage and out of pocket expenditure (OOPE). Insurance penetration and government support remains low in most LMICs. OOPE in healthcare is defined as any direct outlay by households, including gratuities and in-kind payments, where the primary intent is to contribute to the restoration or enhancement of an individual's health. OOPE can include direct medical and direct non-medical costs, but does not include pre-paid fees for health-related taxes or insurance.² OOPEs constitute around 60% of total health expenditure in India⁹ and 67% in Bangladesh.¹⁰ Yet, while some data is available on cost burden of specific conditions such as chronic liver failure¹¹ or organophosphorus poisoning,¹² data on ICU-related OOPE in LMICs remains extremely scarce.

ICU-related OOPEs may rapidly lead to household debt and for some families, cross the threshold into catastrophic health expenditure (**CHE**).^{13,14} The incidence of catastrophic spending on health is reported on the basis of out-of-pocket expenditures exceeding conventional thresholds of 10% or 25% of household total *annual* income.¹⁵ CHE thus refers to any expenditure for medical treatment that can pose a threat towards a household's financial ability to maintain its subsistence needs.³ Across countries, the mean incidence of catastrophic out-of-pocket payments at (considering the 10% threshold) is 9.2%.¹⁵ This incidence was already increasing before the COVID-19 pandemic, with more than one in ten care episodes resulting in catastrophic spending in South Asia in 2010.^{16,17} At the global level in 2010 some 808 million people incurred CHE, with a great concentration in Asia and Africa.

CHE calculation allows to capture financial tensions in households that arise when OOPes are compensated by selling or mortgaging households assets, borrowing money from lenders, banks, black market, friends or relatives during ICU care. Forty-seven percent of patients with septic shock incurred CHE in a Vietnam hospital, against 13% of patients admitted with dengue shock.⁵ In an Indian neonatal ICU, 56% of families incurred CHE, with one out of five families spending more on a single neonatal ICU admission than their monthly income.¹⁸

2.4 Risk factors and coping mechanisms for OOPe and CHE

Coping mechanisms for critical care-related OOPe have been inadequately investigated and are largely unknown for adult ICU patients admitted to LMICs hospitals. Many studies focus on non-ICU populations, limit their scope to direct medical costs or are performed in high-income countries. A study on 3100 households in Dhaka, found that marital status, religion, source of care, access to safe water, income quintile and even the location of households had a significant relationship with OOPe.¹⁰ In a study from Thailand performed on 897 ICU patients with severe sepsis or septic shock, age, nosocomial or ICU infection, admission from the emergency department, number of organ failures, ICU length of stay, and fluid balance the first 72 hours were independently associated with ICU costs, although OOPe were not analyzed.¹⁹ Mechanical ventilation was found to be a factor increasing OOPes in LMICs for pediatric²⁰ patients and total ICU costs in adult patients.^{4,19} Yet, the influence of the initiation of invasive ventilation on CHE remains to be described.

2.5 Impact of costs on ICU care

Financial costs are a barrier to both access and continuation of critical care. In a survey of 1465 ICU physicians from 466 ICUs in 16 Asian countries, those from LMICs (notably China, the Philippines, and Bangladesh) reported as more likely to accede to families' requests to withdraw life sustaining treatments in a patient with an otherwise reasonable chance of survival, so as to avoid further medical bills, than those from high-income economies.¹⁸ The large ACCCOS study on COVID-19 ICU African patients reported 9% of treatment limitation with 3% of withdrawal of therapy, although it was not assessed whether the limitation was influenced by financial motives.²¹ A study in India suggested up to 9% of discharge against medical advice patients are due to financial constraints.²²

2.6 The knowledge gap

In LMICs, where ICU care is increasingly available with limited financial risk protection, there remains limited robust quantitative data linked to OOPes. Particularly, the actual burden that critical illness has on direct and indirect costs to the patients and their families is unknown. While some data on direct costs is starting to be available,⁵⁻⁸ there is limited insight into the magnitude of OOPes and rates of CHE. We also lack robust data on risk factors for CHE due to ICU admissions and coping mechanisms in terms of sources of funding for patient families. Organ support, and especially mechanical ventilation that affects almost one out of two patients in the ICU, may be a key driver of OOPes and CHE rates.

2.7 The present project

This study seeks to precisely quantify ICU care related OOPes in several LMICs in both the private and public sector. Context-specific drivers of OOPes and CHE rates will also be established, while defining coping mechanisms and sources of funding. The impact of organ support, especially invasive mechanical ventilation, will be analyzed as a key potential driver of CHE.

3. STUDY AIMS AND HYPOTHESIS

3.1 Aims

The OOPE study has the following aims:

1. To **quantify** ICU care related OOPE in African and Asian LMICs and the proportion of patients/families facing CHE, comparing patients receiving invasive ventilation to non-ventilated patients.
2. To identify **risk factors** for CHE.
3. To identify **coping strategies** for OOPE and CHE

3.2 Hypothesis

The following exploratory hypothesis are formulated:

- Mechanical ventilation has a doubling effect on CHE incidence.
- The risk of CHE and magnitude of OOPE can be predicted by distinct patient-, disease-, household- and organizational-related factors.
- Distress financing by borrowing from family members is the most frequent coping mechanism both in Asia and Africa.

4. METHODS

4.1 Study design and duration

Observational prospective cohort study.

The recruitment period for each site will be consecutive 14-30 days, based on site feasibility.

Daily follow up until death or ICU discharge.

4.2 Population

All patients admitted to the participating ICUs during a predefined window of 14 days and expected to have a duration of stay >24 hours will be eligible for the study. Exclusion criteria is lack of informed consent. For unconscious or unwell patients the primary caregiver will be approached to answer the interview questions.

4.3 Sample size calculation

Anticipating the following assumptions:

- an expected proportion of ventilated patients of 40% in the study cohort, derived from the aggregate proportion of ventilated patients across CCAA registries in 6 Asian countries (64327 patients across Pakistan, India, Nepal, Malaysia, Vietnam and Bangladesh – of 40.4% and the proportion of ventilated patients in Kenya in 2021-22 (47%, unpublished data).
- expected CHE incidence among ventilated patients of 30%
- expected CHE incidence among non-ventilated patients of 15% (i.e. relative risk of CHE of 0.50)

A sample size of at least 307 patients (at least 184 non ventilated and at least 123 ventilated patients) is needed to verify the expected difference in CHE incidence. Considering a 15% loss to follow-up or incomplete patient episodes, we intend to recruit a total of at least **354 patients** (at least 212 non-ventilated and at least 142 ventilated patients). Assuming each ICU will recruit an average of 12 patients, we seek to enroll at least **30 ICUs in the study, from at least 5 different countries.**

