We will use mixed effects logistic regression models to investigate the relationship between risk factors and CHE. The multivariable mixed effects logistic regression model will then be used to simultaneously estimate the effects of multiple explanatory variables on CHE while controlling for the effects of other covariates. The mixed-effects models will help to account for clustering of the patient level, ICU level and country level data. Tests of significance will be performed at 5 % significance level. Where appropriate, the 95% confidence intervals will be calculated and reported. A detailed Statistical Analysis Plan will be developed for the primary and the secondary outcomes. The Statistical Analysis Plan will be finalized and signed by key investigators after database lock prior to statistical analyses.

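### The target of 354 does not leave the required 307 analysable patients after 15% loss; it appears to come from 307 × 1.15 rather than 307 / 0.85

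*Protocol*

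**What the plan says.** Section 4.3 of the protocol (Sample size calculation) gives the number needed to show the expected difference in CHE incidence: "A sample size of at least 307 patients (at least 184 non ventilated and at least 123 ventilated patients) is needed". The planning assumptions are a 40% share of ventilated patients and CHE incidences of 30% (ventilated) and 15% (non-ventilated).

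The allowance for losses follows: "Considering a 15% loss to follow-up or incomplete patient episodes, we intend to recruit a total of at least" 354, with group minimums given as "at least 212 non-ventilated and at least 142 ventilated patients". The section then assumes an average of 12 recruits per ICU and plans for at least 30 ICUs.

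The study summary (section 1) repeats the inflated target: "at least 354 patients (at least 212 non-ventilated & 142 ventilated patients". The protocol does not show how 307 became 354.

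**The concern.** Loss to follow-up and incomplete episodes can occur only among patients who have been recruited, so the 15% is a fraction of the recruitment target. To keep n analysable patients when a fraction d is lost, one must recruit n / (1 − d). Multiplying by (1 + d) adds 15% of the smaller number and always falls short. Here it adds 47 patients (354 − 307), whereas a 15% loss from 354 removes about 53 (0.15 × 354 = 53.1).

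The recruitment total and both group minimums come from this step, and the planned number of ICUs matches it. If recruitment ends at the stated minimum and losses run at the stated rate, the study misses its own requirement overall and in each group. Incomplete episodes also bear directly on the primary endpoints, because both the cost per complete episode and CHE depend on total episode spending.

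**Working it through.** **Inputs.** Required analysable numbers: 307 = 184 + 123 (section 4.3). Loss: 15% (section 4.3). Recruitment target: 354 = 212 + 142 (section 4.3 and study summary). Recruits per ICU: 12 on average, at least 30 ICUs (section 4.3).

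**Step 1: reproduce the plan's figures, and compare with the correct inflation.**

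| | Required n | n × 1.15 | Rounded up | Protocol target | n / 0.85 | Rounded up |
|---|---|---|---|---|---|---|
| Non-ventilated | 184 | 211.6 | 212 | 212 | 216.47 | 217 |
| Ventilated | 123 | 141.45 | 142 | 142 | 144.71 | 145 |
| Total | 307 | 353.05 | 354 | 354 | 361.18 | 362 |

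Multiplication by 1.15 with rounding up reproduces all three stated targets. Division by 0.85 reproduces none of them. The difference in the total is 362 − 354 = 8 recruits.

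**Step 2: what the stated target delivers at 15% loss.**

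| | Target | Target × 0.85 | Required | Shortfall |
|---|---|---|---|---|
| Non-ventilated | 212 | 180.2 | 184 | 3.8 |
| Ventilated | 142 | 120.7 | 123 | 2.3 |
| Total | 354 | 300.9 | 307 | 6.1 |

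**Step 3: the loss that 354 can absorb.** 1 − 307/354 = 13.3%. By group: 1 − 184/212 = 13.2% and 1 − 123/142 = 13.4%.

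**Step 4: the number of ICUs.** 354/12 = 29.5, which rounds up to the stated 30. 362/12 = 30.2, which rounds up to 31. The planned 30 ICUs at 12 each would give 360 recruits, and 360 × 0.85 = 306, one short of 307.

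**Step 5: effect on power.** Section 4.3 gives no significance level, sidedness or power. Section 4.8 gives 5%. Assuming a two-sided 5% test of 30% against 15%, without continuity correction and without allowance for clustering by ICU or country:

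- 123 ventilated and 184 non-ventilated: power 87.8%.
- 120.7 ventilated and 180.2 non-ventilated: power 87.1%.

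The unrounded difference is about 0.6 percentage points. On the same assumptions and a 1.5:1 ratio, 80% power needs 248 patients (99 + 149) and 85% needs 283 (113 + 170). The roughly 301 patients left after 15% loss exceed both.

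**The case against.** The arithmetic is not in dispute; the case on the other side is that it hardly matters.

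- **The effect is tiny.** No conclusion of the study turns on six analysable patients or 0.6 points of power. This stands, and it limits the weight of the point.
- **The target is a minimum, not a stopping rule.** All eligible admissions in a site's window may be enrolled, and nothing says recruitment stops at 354. This is fair, and actual enrolment may well be higher. But the minimum is the number the protocol offers as sufficient, and at that number its own requirement is missed.
- **The site plan almost closes the gap.** Thirty ICUs at 12 each give 360, which leaves 306. This also stands. The average of 12 is itself an assumption, so a difference of 2 recruits (360 against 362) is within its imprecision, and the case for a 31st ICU is weak. It remains true that 306 is below 307.
- **Not all of the 15% need affect the primary endpoints.** These are measured during the ICU stay, so a patient lost only at the 30-day or 6-month call would still count. The protocol does not split the 15%, so this may soften the consequence but cannot be quantified, and it does not make 354 follow from 307 and 15%.
- **The formula is inferred.** The protocol shows none. The match of all three figures, with rounding up, makes the inference strong. The shortfall does not depend on it, since 354 × 0.85 is below 307 however 354 was obtained.

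**Conclusion.** The point holds. With the protocol's own 307 and 15%, the recruitment target should be 362 (217 + 145), not 354 (212 + 142). The stated target leaves about 301 analysable patients at 15% loss, or equivalently covers a loss of 13.3%. The finding needs only those three figures from section 4.3 and reads the 15% as a fraction of recruited patients. It does not depend on the unstated power or sidedness.

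The size is modest: 8 recruits, about 6 analysable patients and about 0.6 points of power under the assumptions in the working. It is a numerical error in the headline sample size, made in one place and repeated in another. It is worth correcting but does not threaten the study's validity.

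**What to change.** Make the same correction in section 4.3 and in the sample size row of the study summary. There are two acceptable ways:

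1. **Keep 354 (212 + 142) and state what it delivers:** it preserves 307 analysable patients if losses do not exceed 13.3%, or leaves about 301 (roughly 180 + 121) at 15% loss. This costs wording only and is sufficient.
2. **Restate the target as 362 (217 non-ventilated + 145 ventilated).** This costs 8 more recruits. At 12 per ICU the count becomes 31, although 30 ICUs with a marginally higher average would also reach it.

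In either case, add one sentence giving the inflation formula, n / (1 − 0.15), so that the step from 307 to the target can be checked.

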4.4 Study parameters/endpoints

Primary endpoints:

- Costs per complete patient episode, as actually spent in US dollars and International dollars (purchasing power parity exchange rate) in ventilated versus non-ventilated groups.
- Relative risk of CHE in ventilated versus non-ventilated groups.

Secondary endpoints:

- Risk factors for CHE (presumptive list in section 4.6)
- Frequency of different coping strategies for financial coverage of ICU costs

Tertiary endpoints

- Proportion of direct medical versus direct non-medical costs in the total OOPes
- Patient family socio-economic status (SES) or income
- Paying structures, models by country.

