4.6 Data to be collected

CRF structure and timeline is detailed in **Table 1** and comprises sequential domains from A to F. Daily follow up will run until ICU discharge or death, whichever occurs first. An additional telephone follow up at 30 days and 6 months will be used in survivors.

Table 1. CRF structure and timepoints for data collection

	ICU Admission day	Daily (max every 72h)	ICU Discharge	30 days	6 months	Responder
A Socioeconomic status and admission costs	X					Patient or caregiver
B Relative Wealth tool	X					
C Costs form	X	X				
D Discharge form			X			
E Follow up form				☎	☎	Patient or caregiver (telephone)
F Clinical registry Admission form (core) Daily processes of care Discharge (core)	X	X	X			Extracted from patient file

*In some instances daily followup may not be feasible due to unavailability of family members or unwillingness to discuss the study. Therefore a maximum interval of 72h is granted between two daily forms.

#A. Socioeconomic status and admission costs

Absolute household estimated yearly and monthly income will be collected in order to calculate CHE. Household consumption expenditure (food and non-food expenditure) will also be collected in order to minimize recall bias and potential missing income data. This information on expenditure will be used as a proxy of income, in cases where the income information is missing.

The following potential risk factors for CHE will be investigated: household income status, patient occupation; marital status; religion; access to safe water; educational status; ownership and location of households (urban vs. rural vs. slum); female-headed households; household size and age/gender of members; geographical location.¹⁰

#B. Relative wealth

Relative wealth will be quantified using the Equity tool (www.equitytool.org), consisting of a short survey of 11-12 questions allowing to compare the wealth of the respondents to the national or urban population in over 60 countries.

#C. Costs form

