4.8 Statistical analysis

Normally distributed continuous variables will be summarized using means and standard deviations while ordinal variables and skewed continuous data will be expressed as median with interquartile range. For categorical variables, percentages will be calculated and tests of significance between categorical variables will be done using a Fisher's exact or a Chi-square test as appropriate. Student's t-test will be used to compare normally distributed numerical variables between factors and a linear regression model will be fitted where applicable. Mann Whitney U-tests and Kruskal-Wallis tests will be used to compare numerical variables when normality cannot be assumed.

Analysis of the primary endpoint

a. Quantification of ICU OOPes

The primary endpoint will be summarized by reporting overall income group quintiles. Information on direct medical costs, including ICU bed charges, laboratory costs, medication

costs, procedure costs, consumables, medical nutrition, and other related costs will be obtained and summarized.

b. Calculation of CHE

The best method for CHE calculation for single patient episodes is debated in the literature. For the purpose of this study ICU episodes causing CHE will be defined as the calculated total episode OOPE divided by total *yearly* household income exceeding **10%**.²

Other applicable definitions that are justified in literature will also be considered and clearly documented in the Statistical Analysis Plan prior to statistical analysis.

c. CHE Sensitivity analysis

The primary analysis regarding CHE will be repeated using a variety of other considerations as a form of sensitivity analysis. These sensitivity analyses will be clearly outlined in the Statistical Analysis Plan prior to database lock and statistical analysis.

Analysis of risk factors for CHE

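### The hypothesis is worded as an effect of ventilation on CHE, but the primary relative risk names no adjustment for wealth or severity, both recorded at admission

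*Protocol*

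**What the plan says.** Section 3.2 of the protocol lists, among hypotheses labelled exploratory, that ventilation doubles CHE incidence. Section 2.7 describes ventilation as a possible key driver of CHE. The matching primary endpoint in section 4.4 is "Relative risk of CHE in ventilated versus non-ventilated groups".

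Under the primary endpoint, section 4.8 covers the summary of out-of-pocket spending, the CHE definition (episode spending above 10% of yearly household income) and sensitivity analyses of CHE. It names no adjusted estimate. The general methods paragraph says that "tests of significance between categorical variables will be done using a Fisher's exact or a Chi-square test as appropriate".

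Section 4.8 also plans a multivariable mixed-effects logistic model with ICU and country levels, under the heading for CHE risk factors, which is the secondary objective. The candidate factors in section 4.6 (#A) include household income status, education, occupation and housing. They name neither ventilation nor the wealth score.

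Two relevant covariates are already collected. In section 4.6 (#B), "Relative wealth will be quantified using the Equity tool", and Table 1 places that form on the ICU admission day. Form F (#F) records a severity score on admission. On the role of money in treatment, section 2.5 states: "Financial costs are a barrier to both access and continuation of critical care".

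**The concern.** A claim that ventilation doubles CHE is a claim about an effect. A ratio of two group incidences supports it only if the groups are otherwise comparable in what drives CHE, and here there are clear reasons to doubt that.

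- **Wealth.** Income is the denominator of the CHE ratio, so at a given bill a poorer household crosses 10% sooner. If ability to pay also influences who is ventilated, wealth confounds the contrast.
- **Severity.** Sicker patients are more likely to be ventilated and tend to cost more for other reasons, such as longer stay, other organ support and drugs. Part of the crude ratio would then reflect illness rather than ventilation.

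At stake is how the main result is read. A crude ratio well below 2 could be taken as evidence against the hypothesis, and one near or above 2 as confirmation, when either could come from the mix of patients.

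**Working it through.** **1. The plan's own figures.** Section 4.3 assumes CHE of 30% in ventilated and 15% in non-ventilated patients, and "an expected proportion of ventilated patients of 40% in the study cohort". The ventilated versus non-ventilated ratio is 0.30/0.15 = 2.0; the 0.50 printed there is its inverse. The plan states that "A sample size of at least 307 patients (at least 184 non ventilated and at least 123 ventilated patients) is needed". Power is not given. A two-sided 5% test of two proportions with continuity correction and an assumed 85% power needs 124 + 186 = 310, within 3 of 307. At 123 and 184 patients the uncorrected chi-square test has 88% power for 30% versus 15%.

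**2. Set-up (assumed, since the protocol gives no rates by wealth).** Two equal halves, poorer (P) and better-off (B). Non-ventilated CHE is 20% in P and 10% in B, which averages 15%. The true ratio is 2.0 in each half, so ventilated CHE is 40% and 20%. Overall, 40% are ventilated. With vP and vB the proportions ventilated in each half:

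- crude ventilated risk = (vP × 0.40 + vB × 0.20) / (vP + vB)
- crude non-ventilated risk = [(1 − vP) × 0.20 + (1 − vB) × 0.10] / (2 − vP − vB)

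**3. Worked case, vP = 30%, vB = 50%.**

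- Ventilated: (0.30 × 0.40 + 0.50 × 0.20) / 0.80 = 0.220 / 0.80 = 27.5%
- Non-ventilated: (0.70 × 0.20 + 0.50 × 0.10) / 1.20 = 0.190 / 1.20 = 15.8%
- Crude ratio: 0.275 / 0.1583 = 1.74

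Standardised to the whole cohort, the risks are 0.5 × 0.40 + 0.5 × 0.20 = 30% and 0.5 × 0.20 + 0.5 × 0.10 = 15%. The adjusted ratio is 2.0 again.

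**4. Range.**

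| Non-ventilated CHE, P / B | Ventilated, P / B | Crude risks | Crude ratio |
|---|---|---|---|
| 20% / 10% | 40% / 40% | 30.0% / 15.0% | 2.00 |
| 20% / 10% | 35% / 45% | 28.8% / 15.4% | 1.86 |
| 20% / 10% | 30% / 50% | 27.5% / 15.8% | 1.74 |
| 20% / 10% | 25% / 55% | 26.3% / 16.3% | 1.62 |
| 22% / 8% | 30% / 50% | 26.5% / 16.2% | 1.64 |
| 20% / 10% | 45% / 35% | 31.3% / 14.6% | 2.14 |

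In a wider grid (better-off share 20–50%, ventilation 1.25–2 times as common in the better-off, CHE risk 1.5–4 times lower in them) the crude ratio runs from 1.96 down to 1.41. With the ventilation gradient reversed (0.67–0.8 times as common, CHE risk 2–3 times lower, equal halves) it is 2.13–2.35.

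**5. Severity.** The same arithmetic serves with the halves relabelled. If the half with 20% baseline CHE is the more severely ill half and 45% of it is ventilated against 35% of the other, the last row of the table applies and the crude ratio is 2.14. Severity would thus be expected to push away from 1.

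**6. Why the planned logistic model does not close the gap.** As written it yields odds ratios. At 30% versus 15% the odds ratio is (0.30/0.70) / (0.15/0.85) = 2.43, so it cannot be read directly against a doubling of risk.

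**The case against.** The strongest reply is that covariate choice is normally left to the SAP. Section 4.8 promises a detailed SAP for primary and secondary outcomes, and that document is not at hand. The protocol never says that the ratio will be crude only, and its chi-square sentence is a general one. The first aim is to quantify and compare, the hypotheses are labelled exploratory, and a crude ratio is a legitimate description of burden. A covariate-controlled CHE model is planned as well. All this stands, so the fair statement is that no adjustment is named, not that none will be made. What remains is that the protocol fixes an effect-worded hypothesis and a group ratio, and assigns covariate control to a different objective in a model on a different scale.

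Three stronger readings are tempting, and the document does not support them.

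- **That the crude ratio is pulled toward 1.** Section 2.5 concerns access to and continuation of critical care. It gives nothing on starting ventilation in patients already admitted, who are the study population. Better-off families may also spend more, and severity may act the other way.
- **That the study loses power.** If 2.0 were the within-wealth ratio, power at 123/184 would fall to 80%, 70% and 57% for the 1.86, 1.74 and 1.62 rows. But section 4.3 states 30% and 15% as the expected incidences in the two groups. Taken as written, confounding does not lower the power of the crude comparison.
- **That adjusting for wealth alone is enough.** With severity left out, net bias could remain or grow.

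**Conclusion.** The point holds as one of interpretation. The protocol attaches an effect claim to a ventilated versus non-ventilated relative risk with no named confounder set, although wealth and severity are both recorded at admission. The size and direction of bias are unknown. In the illustrations a true ratio of 2.0 appears as 1.41–1.96 when better-off patients are ventilated more often, and as 2.13–2.35 when the gradient is reversed. All of these rest on assumed gradients and on a constant ratio of 2.0 across strata. They show that the crude ratio alone cannot settle whether ventilation doubles CHE; they do not predict what the study will find. The crude ratio remains valid as a description.

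**What to change.** In section 4.8, under the primary endpoint, state that:

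- the ventilated versus non-ventilated relative risk of CHE, and the cost contrast, will also be estimated adjusted for Equity-tool wealth quintile and admission severity score;
- the adjusted relative risk will come from modified Poisson regression, or from standardising a logistic model, allowing for clustering by ICU and country;
- it will be reported beside the crude ratio, and any statement about an effect of ventilation will rest on the adjusted estimate.

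Use the Equity score rather than reported income for the wealth term, because income is already the CHE denominator. Since section 4.6 (#F) allows any of three severity scores, say which will be used or how they will be combined across sites.

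The cost is protocol and SAP wording and a few extra model terms. Both covariates are already collected, so no new data are needed.
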